# 9 STATISTICAL CONSIDERATIONS

#### 9.1 Sample size

The sample size for this trial will be adaptively determined through a phase 2/3 design. Enrollment is planned to last approximately 2 months. Each patient will be randomly allocated to Reparixin or Control according to a randomization ratio of 2:1 and he/she will be followed for the entire treatment and follow-up duration for collecting the efficacy endpoints of each study phase.

For the Phase 2 portion of the study, the primary analysis will compare Reparixin versus Control in terms of time to a composite endpoint (primary endpoint of phase 2) including the following events: requirement of supplemental oxygen treatment, mechanical ventilation use, admission to ICU, and any requirement of rescue medication. Based on clinical experience, an improvement of the median time freedom from composite event of 1.5 times is expected. Assuming an exponential distribution, a total sample size of 48 patients will allow to provide 80% power to show superiority of Reparixin compared to control using a log-rank test at a one-sided significance level of 0.025.

The sample size for the phase 3 is based on assessment of superiority of Reparixin compared to control arm in terms of freedom from a composite endpoint (primary endpoint of phase 3) of severe events including death, admission to the ICU, requirement of mechanical ventilation.

Based on same assumptions of phase 2 regarding randomization (2:1) and expecting to double the median time freedom from severe composite event using Reparixin compared to control (from 2-4 to 4-8 days), a total sample size of 111 patients will allow to achieve a power of 90% to show superiority of Reparixin over control using a log-rank test at a one-sided significance level of 0.025. No drop-out are expected to happen. The number of patients to be included may be revised based on considerations from Phase 2 data analysis.

Primary endpoint of phase 3 will be tested only if superiority of Reparixin is shown in phase 2. Thus, the overall type I error of the study will be controlled at 0.025 via the hierarchical testing procedure.

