#### 9.4.2.2 Primary analysis of phase III

In case of rejection of the null hypothesis H0phaseII, the primary endpoint to assess the efficacy of Reparixin versus the Control in phase III is the time freedom from a severe composite endpoint of events including death, admission to the ICU, mechanical ventilation. The time to the first severe event (any one of the components defined in the phase III composite endpoint) will be used for analysis. In case of no events, the rules for censoring defined in section 9.4.1 will be used.

The primary endpoint will be evaluated by means of Kaplan-Meier estimates and log-rank test. The null hypothesis  $H_{0phaseIII}$  is that the freedom form severe events in Reparixin ( $\Pi_{REPARIXIN}$ ) is lower or equal than control ( $\Pi_{CONTROL}$ ):

H0phaseIII:  $\Pi_{\text{REPARIXIN}} \leq \Pi_{\text{CONTROL}}$ H1phaseIII:  $\Pi_{\text{REPARIXIN}} > \Pi_{\text{CONTROL}}$ 

where  $\Pi_{\text{REPARIXIN}}$  and  $\Pi_{\text{CONTROL}}$  are the freedoms from severe event for Reparixin and Control, respectively.

The null hypothesis H0phaseIII will be rejected, and superiority of Reparixin concluded (alternative hypothesis H1phaseIII) if log-rank p-value will be lower than pre-specified threshold, depending at which analysis (interim or final) the test is performed. Thresholds are calculated according to O'Brien-Fleming spending function boundaries and tare reported in Table 2.

Primary endpoint of phase 3 will be tested only if superiority of Reparixin is shown in phase 2.

Both null hypotheses H0phaseII and H0phaseIII must be rejected in order to claim superiority on Reparixin over Standard of Care. Consequently, no multiplicity correction of type I error will be applied on primary endpoints.

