3.2 Sample size justification

The sample size of the full phase 2/3 study is calculated based on data from clinical experience and on Sponsor expectations as reported in Table 2:

Table 2: Assumptions for primary endpoints

Primary endpoint*	Standard of care (control)	Reparixin
Time to primary endpoint of phase 2	2 days	5 days
Time to primary endpoint of phase 3	2-4 days	4-8 days

* see section 3.5.1.

Based on the following assumptions:

- an enrollment phase of 2 months,

- a total follow-up of 21 days,
- a randomization ratio (reparixin:control) of 2:1
- an exponential distribution for survival probability $S(t) = e^{-\lambda t}$,
- a comparison between treatment by means of a log-rank test,
- an interim analysis framework as described in section 4.5, and
- a correction of the type I and II errors by means of O'Brien-Fleming spending functions

a total of 109 events (corresponding to approximately 111 subjects) will allow to provide >80% power to show superiority of reparixin vs standard of care in terms of primary endpoint of phase 3, controlling the type I error under 0.025.

Based on the same assumptions reported above, phase 2 portion of the study will be performed when a total of 46 events (corresponding to approximately 48 subjects) has happened. This allow to achieve approximately 80% power to show superiority of reparixin vs standard of care in terms of (not severe) primary endpoint of phase 2, controlling the type I error under 0.025.

The remaining portion of the 111 patients will be enrolled in the phase 3 study segment. Anyhow, due to the novel nature of the COVID-19 pandemic and being the primary efficacy endpoint planned in phase 3 not well established, it may require confirmation based on phase 2 data. For this reason, at the end of the phase 2 portion, power calculations may be reassessed, and sample size may be re-estimated for phase 3.

The adaptive design allows for the assessment of efficacy endpoint in phase 2 which are then seamlessly confirmed in the phase 3. Since primary endpoint of phase 3 will be tested only if superiority of reparixin is shown in phase 2 (at interim or final stage), the overall type I error of the study will be controlled at 0.025 via the hierarchical testing procedure.

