7.1 Analysis of primary efficacy endpoints

7.1.1 Testing strategy and multiplicity adjustment

7.1.1.1 Phase 2

The following null hypothesis is defined: the freedom from composite endpoint (section 3.5.1) in reparixin is lower or equal than control:

$$H_0: T_{\text{REPARIXIN}} \leq T_{\text{CONTROL}}$$

$$H_1: T_{\text{REPARIXIN}} > T_{\text{CONTROL}}$$

where $T_{\text{REPARIXIN}}$ and T_{CONTROL} are the freedoms from composite endpoint for reparixin and standard of care, respectively. The null hypothesis H_0 will be rejected, and preliminary (to be confirmed in phase 3) superiority of reparixin shown if log-rank p-value will be lower than pre-specified threshold, depending at which analysis (interim or final) the test is performed. Thresholds are calculated according to O'Brien-Fleming spending function boundaries and are reported in Table 4.

7.1.1.2 Phase 3

The following null hypothesis is defined: that the freedom from severe composite endpoint (section 3.5.1) in reparixin is lower or equal than control:

$$H_0: \Pi_{\text{REPARIXIN}} \leq \Pi_{\text{CONTROL}}$$

$$H_1: \Pi_{\text{REPARIXIN}} > \Pi_{\text{CONTROL}}$$

where $\Pi_{\text{REPARIXIN}}$ and Π_{CONTROL} are the freedoms from severe composite endpoint for reparixin and standard of care, respectively. The null hypothesis will be rejected, and superiority of reparixin concluded if log-rank p-value will be lower than pre-specified threshold, depending at which analysis (first or second interim or final) the test is performed. Thresholds are calculated according to O'Brien-Fleming spending function boundaries and are reported in Table 5.

Phase 3 null and alternative hypotheses will be tested only if superiority of reparixin is shown in phase 2. Null hypotheses of both phases must be rejected in order to claim superiority of reparixin over standard of care. Consequently, no multiplicity correction of type I error will be applied on primary analyses.

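### The protocol's 90% is the power of the phase 3 log-rank test alone; the superiority claim needs both phases to succeed and has about 71–80% power under the SAP's assumptions

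*Protocol*

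**What the plan says.** Protocol 9.1 gives one power for each phase. For phase 2, "a total sample size of 48 patients will allow to provide 80% power to show superiority of Reparixin compared to control", with an expected 1.5-fold improvement in median time. For phase 3, "a total sample size of 111 patients will allow to achieve a power of 90% to show superiority of Reparixin over control", with the median doubled from 2–4 to 4–8 days. The synopsis (Protocol Summary, statistical plan) carries the same two powers. Section 9.1 then sets the gate: "Primary endpoint of phase 3 will be tested only if superiority of Reparixin is shown in phase 2". Section 9.4.2.2 adds that both null hypotheses "must be rejected in order to claim superiority on Reparixin over Standard of Care".

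SAP 3.2 says that "a total of 109 events (corresponding to approximately 111 subjects) will allow to provide >80% power" for the phase 3 primary endpoint. For phase 2 it plans on medians of 2 vs 5 days and 46 events: "This allow to achieve approximately 80% power". SAP 7.1.1 repeats the claim rule: "Null hypotheses of both phases must be rejected in order to claim superiority of reparixin over standard of care".

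Both documents discuss the hierarchy only for type I error. Neither gives the probability that both tests reject.

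**The concern.** When a claim needs two rejections, its power is the probability of both, and that can be no larger than the smaller of the two powers. Phase 2 is planned at about 80%, so a 90% chance of the superiority claim is not available under the plan's own figures. The plan uses the hierarchy to avoid a multiplicity correction but does not state what the hierarchy costs in power.

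At stake is how the planning figure is understood. The 90% stands next to the full 111 patients with no statement that it takes phase 2 success as given. Anyone weighing the chance that the programme ends in a superiority claim has no figure for it, and the most prominent one available is too high for that purpose.

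**Working it through.** **Inputs.** Allocation 2:1, one-sided 0.025, no drop-out (protocol 9.1). Exponential survival, 21 days of follow-up, 46 and 109 events, and the medians (SAP 3.2). Efficacy and futility bounds (SAP Tables 4 and 5). Futility nonbinding (protocol 9.4.5). The 48 phase 2 patients count within the 111 (SAP 3.2).

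**Step 1: event counts.** With N patients and medians mC and mT, expected events at 21 days are N/3 × (1 − 2^(−21/mC)) + 2N/3 × (1 − 2^(−21/mT)).

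- Phase 2, 2 vs 5 days, N = 48: 15.99 + 30.26 = 46.2. The SAP has 46.
- Phase 3, 2 vs 4 days, N = 111: 36.97 + 72.06 = 109.0. The SAP has 109.
- Phase 3, 4 vs 8 days, N = 111: 36.03 + 62.00 = 98.0.

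**Step 2: the plan's own powers.** The log-rank drift is |ln HR| × √(events × 2/9), and fixed-design power is Φ(drift − 1.960). The group-sequential figures are simulated with the SAP bounds (1–2 million runs).

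| Test | Drift | Fixed design | Futility followed | Futility ignored |
|---|---|---|---|---|
| Phase 2, HR 2/5 = 0.4, 46 events | 0.916 × √10.22 = 2.930 | 83.4% | 80.1% | 83.1% |
| Phase 3, HR 0.5, 109 events | 0.693 × √24.22 = 3.411 | 92.7% | 90.3% | 92.1% |

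So the stated 80% and 90% both reproduce, each as the power of one test taken alone.

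**Step 3: bounds from the stated powers.** From 80% and 90%, the probability that both reject is at least 0.80 + 0.90 − 1 = 70% and at most 80%. If the tests were independent it would be 0.80 × 0.90 = 72%.

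**Step 4: power of the claim.** The phase 2 patients contribute to both tests, and both composites contain ICU admission and invasive ventilation, so the statistics are likely to be correlated. The documents give no correlation. I therefore vary the within-patient correlation r between the two endpoints from 0 to 1. This is an assumption. At r = 1 the two final statistics correlate at only about √(46/109) = 0.65, because the later patients enter phase 3 alone.

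| Phase 3 scenario | Futility | r = 0 | r = 0.5 | r = 1 |
|---|---|---|---|---|
| 109 events | followed | 72.3% | 74.3% | 77.2% |
| 109 events | ignored | 76.6% | 78.1% | 80.3% |
| 98 events | followed | 70.6% | 72.8% | 75.8% |
| 98 events | ignored | 74.1% | 76.0% | 78.6% |

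The 98-event rows keep the interims at 60 and 81 events; phase 3 alone then has 88.2% power with futility followed. Moving the interims to 55% and 74% of 98 events (54 and 73) gives 87.1% alone and lowers the smallest joint figure to 69.8%.

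**Step 5: marginal is not conditional.** Power of phase 3 given phase 2 success is the joint figure divided by phase 2 power. With futility followed this is 72.3/80.1 = 90% to 77.2/80.1 = 96% at 109 events, and 70.6/80.1 = 88% to 75.8/80.1 = 95% at 98 events. With futility ignored it reaches 80.3/83.1 = 97%. The marginal 88–90% should therefore not be labelled as power given phase 2 success.

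**Step 6: the protocol's phase 2 effect.** A ratio of medians of 1.5 is HR 0.667. With 46 events the drift is 0.405 × √10.22 = 1.296 and fixed-design power is 25.3%. With the Table 4 bounds it is 23.1% (futility followed) or 25.1% (ignored). The joint figure is then about 21–25%. A phase 2 power of 80% at that effect would need 215 events.

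**The case against.** The strongest reply is that nothing has been miscalculated. The 90% reproduces at 90.3%, and the SAP's figure is conservative. Both belong to a single test, and the SAP limits its figure to that test: 109 events "will allow to provide >80% power to show superiority of reparixin vs standard of care in terms of primary endpoint of phase 3". Protocol 9.1 lists 80% and 90% separately and states the gate straight afterwards. Giving a power for each gated test is common practice. All of this stands, so the point is one of labelling and of a missing figure.

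A reader might infer that the plan promises 90% power for the programme, and so a 10% risk of failure against which 20–29% can be set. The documents do not support that. No section calls the 90% a programme power, and neither document states a 10% failure risk.

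Nor is the contrast with the SAP strong. Futility is nonbinding, and with it ignored the joint figure reaches 80.3%, so the SAP's figure is narrowly missed at most.

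Two further replies carry some weight. First, the 98-event case rests on the SAP's 21 days. Protocol 7.1 allows up to 31 days in the study, and at 28–31 days the 4 vs 8 day medians give 104–106 events. Second, the phase 3 size and endpoint may be revised after phase 2, so the 111 patients and 90% are provisional. More phase 3 patients would raise the marginal power, but they cannot lift the power of the claim above that of phase 2.

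**Conclusion.** The concern holds as a matter of what the 90% describes. It is the marginal power of the phase 3 log-rank test, and the superiority claim defined in both documents has lower power, limited by phase 2 at roughly 80%. Under the SAP's assumptions, the claim's power is about 72–77% with futility followed and 77–80% with it ignored. With 4 vs 8 day medians and 21 days of follow-up it is about 71–79%.

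The cap follows from the claim rule and the stated phase 2 power, with no modelling. The position within the range depends on the endpoint correlation, which the documents do not give, and on whether the nonbinding futility bounds are followed. The whole range depends on the SAP's 2 vs 5 days for phase 2. The protocol's 1.5-fold improvement may have been meant as an increase of 1.5 times the control median, which takes 2 days to 5. As worded, it can also be read as a ratio of medians, and the claim's power is then capped at about 25%.

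**What to change.** First reconcile the phase 2 effect: the protocol's 1.5-fold improvement (9.1 and synopsis) and the SAP's 2 vs 5 days should be stated as one pair of medians or one hazard ratio. Until that is done, an overall power written into protocol 9.1 would sit beside an assumption that may contradict it.

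Then, in protocol 9.1, the synopsis and SAP 3.2:

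- Label the existing figures as marginal powers: phase 2 log-rank about 80%; phase 3 log-rank alone about 88–90% across the stated medians, with futility followed.
- Add that superiority requires both rejections and that the overall power of that claim is about 71–80%, conditional on 2 vs 5 days in phase 2. State the endpoint correlation and futility assumptions behind the range.

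If 2 vs 5 days is confirmed, the cost is wording only, with no change to patients, boundaries or tests; the overall figure is less favourable than the one now shown. If the 1.5-fold ratio is the intended effect, the phase 2 size itself has to be revisited.

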## 9.2 Overview of planned statistical analyses

The study plans for the following statistical analyses:

- Phase II analysis: this analysis will be conducted when all planned enrolled subjects for phase II have reached the primary composite endpoint of phase II and the study database has been (interim) locked.
- Phase III analysis: in case of success of phase II, this analysis will be conducted when all planned enrolled subjects for phase III have reached the primary composite endpoint of phase III and the study database has been locked.
- Analyses for the Data Monitoring Committee: these analyses will be produced periodically

## 9.3 Analysis Population

The following population will be defined:

• The Safety (SAF) population will consist of all randomized patients who received at least one dose of the investigational product (either Reparixin or Standard of Care). Safety population will be analyzed according to the actual treatment received. The SAF population will be used to present results on safety data.

- The Full Analysis Set (FAS) population will consist of all randomized patients who received at least one dose of the investigational product (either Reparixin or Standard of Care). FAS population will be analyzed according to ITT principle, i.e. by treatment allocation. The FAS population will be used for the primary analyses of the study and to present results on efficacy data.
- The Per Protocol (PP) population will consist of all randomized patients who received at least one dose of the investigational product and do not have Major Protocol Deviations. The PP population will be used for sensitivity analyses.

## 9.4 Statistical Methodology

# 9.4.1 General Considerations

This trial's design will allow for adaptations based but not limited to the following:

- Interruption of an experimental treatment route of administration in favour of the other due to safety reasons;
- Confirmation or modification of the primary, secondary and exploratory endpoints;
- Confirmation or modification of the sample size for the Phase 3 segment;
- Early closure of the study for efficacy, futility or safety reasons.

All study adaptation will be carefully detailed in the Statistical Analysis Plan and in the Clinical Study Report.

Appropriate descriptive statistics will be produced by treatment arms and by route of administration of Reparixin, according to the nature of the variable. For continuous data, number of observations, mean, standard deviation, median and range (minimum and maximum) will be presented. For qualitative data, frequency distributions and percentages per category will be presented. If appropriate, confidence intervals around the mean or the proportions will be presented. The number of subjects with missing data will be presented under the "Missing" category. Missing values will not be included in the denominator count when computing percentages. When continuous data will be summarized, only the non-missing values will be evaluated for computing summary statistics. Any exception will be declared.

For time-to-event variables, cumulative freedom from event will be evaluated using Kaplan-Meier method. The degree of uncertainty will be expressed with 95% confidence limits (calculated per the method proposed by Greenwood). Comparison of curves among arms will be performed with the log-rank test. Kaplan-Meier graphs will be presented along with the number of patient-at-risk at exact time points. Subjects ongoing and who are free from event at the analysis cut-off date will be censored at the analysis cut-off date. Subjects who have discontinued without an event will be censored at the date of discontinuation.

Unless otherwise specified, the significance level used for statistical testing will be 0.05 and two-sided tests will be used. All patient data collected on the CRF will be listed by patient and centre.

The Statistical Analysis Plan will be issued before the database lock with more technical and detailed elaboration of the principal features of statistical analyses. Additional post-hoc analysis may be produced to further allow comparison between treatment and control, according to the results obtained. Any deviations from the original statistical plan (including unplanned analyses) will be documented in the Clinical Study Report.

### 9.4.2 Analysis of efficacy variables

#### 9.4.2.1 Primary analysis of phase II

In phase II, the primary endpoint to assess the efficacy of Reparixin versus the Control is the time freedom from a composite endpoint of events including supplemental oxygen treatment, mechanical ventilation use, admission to ICU, and any use of rescue medication. The time to the first event (any one of the components defined in the phase II composite endpoint) will be used for analysis. In case of no events, the rules for censoring defined in section 9.4.1 will be used.

The primary endpoint will be evaluated by means of Kaplan-Meier estimates and log-rank test. The null hypothesis H0phaseII is that the freedom form events in Reparixin (TREPARIXIN) is lower or equal than control (TCONTROL):

H0phaseII: TREPARIXIN ≤ TCONTROL H1phaseII: TREPARIXIN > TCONTROL

where TREPARIXIN and TCONTROL are the freedoms from event for Reparixin and Control, respectively. The null hypothesis H0phaseII will be rejected, and superiority of Reparixin concluded (alternative hypothesis H1phaseII) if log-rank p-value will be lower than pre-specified threshold, depending at which analysis (interim or final) the test is performed. Thresholds are calculated according to O'Brien-Fleming spending function boundaries and tare reported in Table 1.

#### 9.4.2.2 Primary analysis of phase III

In case of rejection of the null hypothesis H0phaseII, the primary endpoint to assess the efficacy of Reparixin versus the Control in phase III is the time freedom from a severe composite endpoint of events including death, admission to the ICU, mechanical ventilation. The time to the first severe event (any one of the components defined in the phase III composite endpoint) will be used for analysis. In case of no events, the rules for censoring defined in section 9.4.1 will be used.

The primary endpoint will be evaluated by means of Kaplan-Meier estimates and log-rank test. The null hypothesis  $H_{0phaseIII}$  is that the freedom form severe events in Reparixin ( $\Pi_{REPARIXIN}$ ) is lower or equal than control ( $\Pi_{CONTROL}$ ):

H0phaseIII:  $\Pi_{\text{REPARIXIN}} \leq \Pi_{\text{CONTROL}}$ H1phaseIII:  $\Pi_{\text{REPARIXIN}} > \Pi_{\text{CONTROL}}$ 

where  $\Pi_{\text{REPARIXIN}}$  and  $\Pi_{\text{CONTROL}}$  are the freedoms from severe event for Reparixin and Control, respectively.

The null hypothesis H0phaseIII will be rejected, and superiority of Reparixin concluded (alternative hypothesis H1phaseIII) if log-rank p-value will be lower than pre-specified threshold, depending at which analysis (interim or final) the test is performed. Thresholds are calculated according to O'Brien-Fleming spending function boundaries and tare reported in Table 2.

Primary endpoint of phase 3 will be tested only if superiority of Reparixin is shown in phase 2.

Both null hypotheses H0phaseII and H0phaseIII must be rejected in order to claim superiority on Reparixin over Standard of Care. Consequently, no multiplicity correction of type I error will be applied on primary endpoints.

